#### Further information

- Clinicaltrials.gov identifier for the main trial: NCT03506789
- Clinicaltrials.gov identifier for this subgroup analyses: NCT05008367
- Published protocol article for the main trial: <https://doi.org/10.1111/aas.13481>
- Published statistical analyses plan for the main trial: <https://doi.org/10.1111/aas.13560>

## Simulated data

```
#Number of participants
n_part <- 485
df <- NULL

#Random assignment to the three groups
df$group <- as.factor(sample(c(1:3),n_part, replace=TRUE))

#Random assignment to the sites
df$site <- sample(c("A","B","C"),n_part, replace=TRUE)

#Random assignment to age
df$bc_age <- rnorm(n_part, mean=65, sd=8)
df$bc_ASA_above_2 <- sample(c(0,1),n_part, replace=TRUE)
df$bc_High_pain_at_rest <- rnorm(n_part, mean=30, sd=10)
df$bc_High_pain_when_active <- rnorm(n_part, mean=30, sd=10)
df$bc_Only_spinal <- sample(c(0,1),n_part, replace=TRUE)
df$bc_Prior_pain_med <- sample(c(0,1),n_part, replace=TRUE)
df$bc_BMI <- rnorm(n_part, mean=30, sd=4)

df <- data.frame(df)
df$age <- 0
df$age[df$bc_age > 65] <- 1

df_mc <- df

#The simulated outcome depending on the median for each group:
n_dd <- 35
n_dp <- 38
n_pp <- 43
df$outcome[df$group==1] <- rnorm(sum((df$group==1)*1),mean=n_dd,sd=5)
df$outcome[df$group==2] <- rnorm(sum((df$group==2)*1),mean=n_dp,sd=5)
df$outcome[df$group==3] <- rnorm(sum((df$group==3)*1),mean=n_pp,sd=5)

#The simulated RRR of age:
rrr_age <- 0.1
df$outcome[df$age == 1] <- df$outcome[df$age == 1]-df$outcome[df$age == 1]*rrr_age
```

## Baseline characteristics for subgroup

```
library(tableone)
CreateTableOne(c("bc_age", "bc_BMI", "bc_ASA_above_2", "bc_High_pain_at_rest", "bc_High_pain_when_active",
                "bc_Only_spinal", "bc_Prior_pain_med"), strata = c("age", "group"),
              factorVars = c("bc_ASA_above_2", "bc_Only_spinal", "bc_Prior_pain_med"),
              data=df, test=FALSE)
```

```
##                               Stratified by age:group
##                               0:1           1:1
##  n                               81           76
##  bc_age (mean (SD))              58.40 (4.65) 71.01 (4.90)
##  bc_BMI (mean (SD))              30.00 (3.79) 29.30 (3.79)
##  bc_ASA_above_2 = 1 (%)           41 (50.6)  45 (59.2)
##  bc_High_pain_at_rest (mean (SD)) 29.28 (9.40) 30.50 (9.56)
##  bc_High_pain_when_active (mean (SD)) 31.05 (10.00) 29.55 (8.84)
##  bc_Only_spinal = 1 (%)           38 (46.9)  36 (47.4)
##  bc_Prior_pain_med = 1 (%)         39 (48.1)  34 (44.7)
##                               Stratified by age:group
##                               0:2           1:2
##  n                               71           78
##  bc_age (mean (SD))              59.49 (4.42) 70.93 (4.92)
##  bc_BMI (mean (SD))              29.95 (4.24) 29.99 (4.23)
##  bc_ASA_above_2 = 1 (%)           27 (38.0)  38 (48.7)
##  bc_High_pain_at_rest (mean (SD)) 32.68 (12.43) 31.61 (10.56)
##  bc_High_pain_when_active (mean (SD)) 29.73 (9.50) 30.52 (10.82)
##  bc_Only_spinal = 1 (%)           36 (50.7)  35 (44.9)
##  bc_Prior_pain_med = 1 (%)         28 (39.4)  37 (47.4)
##                               Stratified by age:group
##                               0:3           1:3
##  n                               86           93
##  bc_age (mean (SD))              58.59 (4.81) 71.68 (4.97)
##  bc_BMI (mean (SD))              29.53 (3.67) 30.12 (3.97)
##  bc_ASA_above_2 = 1 (%)           41 (47.7)  42 (45.2)
##  bc_High_pain_at_rest (mean (SD)) 31.73 (9.62) 30.29 (9.94)
##  bc_High_pain_when_active (mean (SD)) 30.49 (11.03) 29.38 (9.56)
##  bc_Only_spinal = 1 (%)           41 (47.7)  42 (45.2)
##  bc_Prior_pain_med = 1 (%)         43 (50.0)  47 (50.5)
```

## Quantile regression for interaction only

```
#https://cran.r-project.org/web/packages/quantreg/vignettes/rq.pdf  
#install.packages("quantreg")  
suppressMessages(suppressWarnings(library(quantreg)))  
fit_rq <- rq(outcome ~ group*age,data=df)
```

```
## Warning in rq.fit.br(x, y, tau = tau, ...): Solution may be nonunique
```

```
summary(fit_rq,se="nid")
```

```
##  
## Call: rq(formula = outcome ~ group * age, data = df)  
##  
## tau: [1] 0.5  
##  
## Coefficients:  
##           Value      Std. Error t value Pr(>|t|)  
## (Intercept) 34.64455   0.62947   55.03749 0.00000  
## group2      3.65202   1.23630    2.95398 0.00329  
## group3      8.70705   1.00415    8.67107 0.00000  
## age        -3.10804   0.82288   -3.77702 0.00018  
## group2:age -0.47171   1.46960   -0.32098 0.74837  
## group3:age -1.31063   1.23464   -1.06155 0.28897
```

```
#https://www.rdocumentation.org/packages/aod/versions/1.3.1/topics/wald.test  
#install.packages("aod")  
suppressMessages(suppressWarnings(library(aod)))  
#https://www.rdocumentation.org/packages/Zelig/versions/5.1.7/topics/vcov_rq  
#install.packages("Zelig")  
suppressMessages(suppressWarnings(library(Zelig)))  
wald.test(b = coef(fit_rq), Sigma = vcov_rq(fit_rq), Terms = 5:6)
```

```
## Wald test:  
## -----  
##  
## Chi-squared test:  
## X2 = 1.1, df = 2, P(> X2) = 0.57
```

## Van Elteren p-values

```
#https://cran.r-project.org/web/packages/sanon/sanon.pdf
#install.packages("sanon")
suppressMessages(suppressWarnings(library(sanon)))

df_test <- df[df$age == 0 & (df$group == "1" | df$group == "2"),]
summary(sanon(outcome ~ grp(group, ref="1") + str(site), data=df_test))
```

```

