## Statistical methods

Statistical analyses will be carried out using R (R Core Team, Vienna, Austria) and Stata (StataCorp LLC, Texas, USA) by two independent statisticians ([name] and [name]). The two statisticians will independently prepare a statistical report, which will be compared for any discrepancies. The discrepancies will be logged, and any changes for the final report will be described. The final report, the two original reports, and the discrepancies log, will be approved by the co-authors. All reports will be added as supplemental material in the final paper.

We will perform pairwise comparisons of the three groups, i.e., three comparisons. We plan to test for subgroup heterogeneity of the intervention effect by assessing whether the interaction between the subgroup and the treatment group is significantly different. We will use quantile regression adjusted for site to test for significant interaction between the predefined dichotomized subgroups and treatment group using a threshold of 0.05 for subsequent Wald test.

We will assess the effects of dexamethasone for each of the predefined subgroups analyzed separately using van Elteren test adjusted for site. As these subgroup analyses will be interpreted as exploratory, and with the purpose of generating hypotheses, we will use the same threshold for significance as used in the main trial. The threshold for significance will therefore be multiplicity corrected using Bonferroni correction and is based on the three groups. Thus, the level of significance will be 0.017. We will quantify and report differences between the groups using Hodges-Lehmann median difference and the corresponding 98.3% confidence intervals.

The subgroup analyses will be presented in forest plots.

Attached is an example of the planned analyses for one subgroup analysis (**Supplemental Material**)

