##      Estimate Std.Err Chisq Pr(>Chisq)
## outcome   0.1707  0.0455  14.1   0.00017 ***
## ---
## Signif. codes:  0 '***' 0.001 '**' 0.01 '*' 0.05 '.' 0.1 ' ' 1

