##      Estimate Std.Err Chisq Pr(>Chisq)
## outcome   0.3992  0.0242   273   <2e-16 ***
## ---
## Signif. codes:  0 '***' 0.001 '**' 0.01 '*' 0.05 '.' 0.1 ' ' 1

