##      Estimate Std.Err Chisq Pr(>Chisq)
## outcome   0.2663  0.0377   49.8   1.7e-12 ***
## ---
## Signif. codes:  0 '***' 0.001 '**' 0.01 '*' 0.05 '.' 0.1 ' ' 1

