##           Estimate Std.Err Chisq Pr(>Chisq)
## outcome    0.1978  0.0443  19.9    8.1e-06 ***
## ---
## Signif. codes:  0 '***' 0.001 '**' 0.01 '*' 0.05 '.' 0.1 ' ' 1

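### The code headed Van Elteren p-values runs a Wald test of a site-stratified Mann-Whitney estimate, not the van Elteren test named in the methods

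*Combined protocol and SAP*

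**What the plan says.** The Statistical methods section plans to compare the three groups pairwise within each level of each predefined subgroup using the "van Elteren test adjusted for site". The significance level is 0.017, from a Bonferroni correction for three groups. Two statisticians work independently, one report is compared with the other, and "The discrepancies will be logged, and any changes for the final report will be described". The status of the results is also stated: "As these subgroup analyses will be interpreted as exploratory". The section then points to the Supplemental Material as an example of the planned analyses for one subgroup.

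In that supplement, the block headed Van Elteren p-values makes six calls of the form "summary(sanon(outcome ~ grp(group, ref='1') + str(site), data=df_test", three for each age level. Each output row gives an estimate, a standard error, a chi-square and a p-value. A note says that the estimate is the Mann-Whitney probability minus 0.5. Four of the six rows begin "0.1707 0.0455 14.1", "0.3992 0.0242 273", "0.2663 0.0377 49.8" and "0.1978 0.0443 19.9". The other two give 0.4040, 0.0234, 297 and 0.2445, 0.0392, 39. Nothing in the document as provided says that this output differs from a van Elteren test.

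**The concern.** A van Elteren test ranks within site, weights the sites by 1/(site size + 1), and divides by a variance that holds under the null. Without ties, that variance depends on the sample sizes alone. The printed standard errors do not behave that way: they range from 0.0455 down to 0.0234 although the arm sizes hardly differ.

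The plan has 7 subgroups × 2 levels × 3 comparisons = 42 within-subgroup p-values, and the template would govern all of them. If both statisticians follow it, the paper reports a test that was not run. If the second statistician programs a true van Elteren test in Stata, the two sets of p-values will differ. The log would probably show this, but the plan does not say which test then prevails, so the choice would be made with results in view.

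**Working it through.** **Inputs.** Arm sizes come from the supplement's baseline table: 81, 71 and 86 for groups 1, 2 and 3 at age 65 or below, and 76, 78 and 93 above 65. Estimates, standard errors and chi-squares come from the Van Elteren p-values output. The simulated outcome is continuous normal with three randomly assigned sites (Simulated data), so there are no ties.

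**Step 1: reproduce the printed statistic.** Compute W = (estimate/SE)². For group 1 v 3, age 65 or below: (0.3992/0.0242)² = 272.1, printed 273. Rounding of the two inputs allows 270.9 to 273.3. For the same comparison above 65: (0.4040/0.0234)² = 298.1, printed 297, allowed range 296.7 to 299.4. All six rows agree within rounding, so the printed chi-square is a Wald statistic.

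**Step 2: the largest possible van Elteren statistic.** In site h, let w_h = n1h·n2h/(N_h + 1).

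- The statistic is [Σ w_h(θ_h − 0.5)]² / (Σ w_h/12), where θ_h is the Mann-Whitney probability in site h.
- With complete separation in every site, each term θ_h − 0.5 equals 0.5, and the statistic reaches (Σ w_h)²/4 ÷ (Σ w_h/12) = 3·Σ w_h.
- For any split over sites this is at most 3·n1·n2/N.
- For 81 v 86: 3 × 81 × 86/167 = 125.1. For 76 v 93: 3 × 76 × 93/169 = 125.5. With three equal sites the maxima are 122.9 and 123.3.

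The printed 273 and 297 are therefore impossible for this test. Other site weights do not help: by the Cauchy-Schwarz inequality, any weighting of the site statistics with its null variance has the same upper bound.

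**Step 3: the standard error under the null.** Unstratified, it is √[(N + 1)/(12·n1·n2)]. For 81 v 86: √[168/(12 × 81 × 86)] = 0.0448, against 0.0242 printed. The last column of the table divides the printed estimate by this null SE and squares it. The value in brackets assumes three equal sites, with N + 3 in place of N + 1.

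| Age, groups | n1 v n2 | Printed SE | Null SE | Printed χ² | (Est/SE)² | Ceiling 3·n1·n2/N | χ² with null SE |
|---|---|---|---|---|---|---|---|
| ≤65, 1 v 2 | 81 v 71 | 0.0455 | 0.0471 | 14.1 | 14.1 | 113.5 | 13.1 (13.0) |
| ≤65, 1 v 3 | 81 v 86 | 0.0242 | 0.0448 | 273 | 272.1 | 125.1 | 79.3 (78.4) |
| ≤65, 2 v 3 | 71 v 86 | 0.0377 | 0.0464 | 49.8 | 49.9 | 116.7 | 32.9 (32.5) |
| >65, 1 v 2 | 76 v 78 | 0.0443 | 0.0467 | 19.9 | 19.9 | 115.5 | 18.0 (17.7) |
| >65, 1 v 3 | 76 v 93 | 0.0234 | 0.0448 | 297 | 298.1 | 125.5 | 81.4 (80.5) |
| >65, 2 v 3 | 78 v 93 | 0.0392 | 0.0445 | 39 | 38.9 | 127.3 | 30.3 (29.9) |

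The printed SE is 0.97 of the null SE for the smallest estimate and 0.52 of it for the largest. That is a variance estimated away from the null.

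**Step 4: consequence for type I error.** Each setting had 20,000 simulated null trials with a normal outcome, three random sites and a nominal level of 1.7% (Monte Carlo error about 0.1 percentage point). The package itself was not run. A standard non-null Mann-Whitney variance, with site weights w_h, stands in for it.

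| Size per arm | Wald | van Elteren |
|---|---|---|
| 71–93 (the six documented pairs), mean | 1.88% | 1.69% |
| 40 (assumed) | 2.1% | 1.7% |
| 30 (assumed) | 2.3% | 1.6% |
| 20 (assumed) | 2.7% | 1.7% |
| 12 (assumed) | 4.0% | 1.3% |

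At the documented sizes the two tests reached different decisions in 0.2–0.3% of trials.

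**The case against.** The best defence is that this is a matter of labelling. Both procedures address the same site-stratified Mann-Whitney contrast and differ in the variance used. At the documented sizes their error rates and decisions are almost the same, and the analyses are exploratory, with heterogeneity tested separately by quantile regression. All of that stands, and it limits the severity.

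The larger error rates rest on assumed sizes and on a stand-in for the package. That also stands. They show what could happen in a sparse subgroup level, not what will happen in this trial.

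A null variance is also not always better calibrated. If arms share a location but differ in spread, the order can reverse. In 8,000 simulated trials with an assumed SD ratio of 3 at 81 v 86, Wald rejected 2.1% and van Elteren 2.5%. With 60 v 100 and an assumed doubled SD in the smaller arm, the figures were 2.1% and 3.3%. So the case for van Elteren is that the plan names it, not that it is superior throughout.

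Finally, the supplement is only an example, and its quantile regression call already omits the site term that the methods require. A reader may fairly take the methods text as controlling. Even so, the plan does not say so, and the example is the only code that shows how the named test would be run. The logging procedure makes a silent switch unlikely but does not settle which test to report. The main-trial SAP, cited under Further information, was not available and might bear on the choice. It would not change what this code computes.

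**Conclusion.** The mismatch is certain. It follows from the printed figures, the printed arm sizes and the van Elteren formula, and needs no knowledge of the package. Two of the six chi-squares are more than twice the attainable maximum, and all six are Wald statistics.

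The practical effect in the example is small. All six comparisons stay far below 0.017, and the weakest moves from p = 0.00017 to about 0.0003. At 71 to 93 per arm, type I error rises by about 0.2 percentage points (1.88% − 1.69%). A material excess over 1.7% arises only if real subgroup levels are small, and it is conditional on the assumptions in step 4. Because the analyses are exploratory, this should be corrected before analysis but does not undermine the plan.

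**What to change.** Make the named test and the executed test the same before the data are analysed.

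- **Preferred, because it keeps to the governing text:** take the p-value from a van Elteren test with ranks within site, site weights 1/(N_h + 1) and a tie-corrected null variance. Keep the sanon Mann-Whitney estimate as a descriptive quantity. Check on the simulated data that R and Stata return the same p-values.
- **Sufficient:** if the sanon test is kept, describe it in Statistical methods and in the supplement heading as a Wald test of the site-stratified Mann-Whitney estimate. Require it in both statisticians' reports, and note that its error rate may exceed 0.017 in small subgroup levels.

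The first option costs a few lines of code and slightly less favourable p-values. The second costs one sentence and one heading.

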## Call:
## sanon.formula(formula = outcome ~ grp(group, ref = "1") + str(site),
##   data = df_test)
##
##
##      Estimate Std.Err Chisq Pr(>Chisq)
## outcome   0.1707  0.0455  14.1   0.00017 ***
## ---
## Signif. codes:  0 '***' 0.001 '**' 0.01 '*' 0.05 '.' 0.1 ' ' 1
## Note that the estimates of responses are for the (MW estimate - 0.5).
```

```
df_test <- df[df$age == 0 & (df$group == "1" | df$group == "3"),]
summary(sanon(outcome ~ grp(group, ref="1") + str(site), data=df_test))
```

```
## Call:
## sanon.formula(formula = outcome ~ grp(group, ref = "1") + str(site),
##   data = df_test)
##
##
##      Estimate Std.Err Chisq Pr(>Chisq)
## outcome   0.3992  0.0242   273   <2e-16 ***
## ---
## Signif. codes:  0 '***' 0.001 '**' 0.01 '*' 0.05 '.' 0.1 ' ' 1
## Note that the estimates of responses are for the (MW estimate - 0.5).
```

```
df_test <- df[df$age == 0 & (df$group == "2" | df$group == "3"),]
summary(sanon(outcome ~ grp(group, ref="2") + str(site), data=df_test))
```

```
## Call:
## sanon.formula(formula = outcome ~ grp(group, ref = "2") + str(site),
##   data = df_test)
##
##
##      Estimate Std.Err Chisq Pr(>Chisq)
## outcome   0.2663  0.0377   49.8   1.7e-12 ***
## ---
## Signif. codes:  0 '***' 0.001 '**' 0.01 '*' 0.05 '.' 0.1 ' ' 1
## Note that the estimates of responses are for the (MW estimate - 0.5).
```

```
df_test <- df[df$age == 1 & (df$group == "1" | df$group == "2"),]
summary(sanon(outcome ~ grp(group, ref="1") + str(site), data=df_test))
```

```
## Call:
## sanon.formula(formula = outcome ~ grp(group, ref = "1") + str(site),
##   data = df_test)
##
##
##           Estimate Std.Err Chisq Pr(>Chisq)
## outcome    0.1978  0.0443  19.9    8.1e-06 ***
## ---
## Signif. codes:  0 '***' 0.001 '**' 0.01 '*' 0.05 '.' 0.1 ' ' 1
## Note that the estimates of responses are for the (MW estimate - 0.5).
```

```
df_test <- df[df$age == 1 & (df$group == "1" | df$group == "3"),]
summary(sanon(outcome ~ grp(group, ref="1") + str(site), data=df_test))
```

```
## Call:
## sanon.formula(formula = outcome ~ grp(group, ref = "1") + str(site),
##   data = df_test)
##
##
##           Estimate Std.Err Chisq Pr(>Chisq)
## outcome    0.4040  0.0234   297    <2e-16 ***
## ---
## Signif. codes:  0 '***' 0.001 '**' 0.01 '*' 0.05 '.' 0.1 ' ' 1
## Note that the estimates of responses are for the (MW estimate - 0.5).
```

```
df_test <- df[df$age == 1 & (df$group == "2" | df$group == "3"),]
summary(sanon(outcome ~ grp(group, ref="2") + str(site), data=df_test))
```

```
## Call:
## sanon.formula(formula = outcome ~ grp(group, ref = "2") + str(site),
##   data = df_test)
##
##
##           Estimate Std.Err Chisq Pr(>Chisq)
## outcome    0.2445  0.0392    39    4.2e-10 ***
## ---
## Signif. codes:  0 '***' 0.001 '**' 0.01 '*' 0.05 '.' 0.1 ' ' 1
## Note that the estimates of responses are for the (MW estimate - 0.5).
```

## Hodges-Lemann median differences

```
#https://rdrr.io/cran/DescTools/man/HodgesLehmann.html  
#install.packages("DescTools")  
suppressMessages(suppressWarnings(library("DescTools")))
```

```
#Sammenligning mellem aldersgrupper i hver gruppe  
HodgesLehmann(df$outcome[df$group == 1 & df$age == 0],  
              df$outcome[df$group == 2 & df$age == 0],  
              conf.level = 0.983)
```

```
##      est      lwr.ci      upr.ci  
## -3.0577938 -5.1431926 -0.9508709
```

```
HodgesLehmann(df$outcome[df$group == 1 & df$age == 0],  
              df$outcome[df$group == 3 & df$age == 0],  
              conf.level = 0.983)
```

```
##      est      lwr.ci      upr.ci  
## -8.405907 -10.300894 -6.602105
```

```
HodgesLehmann(df$outcome[df$group == 2 & df$age == 0],  
              df$outcome[df$group == 3 & df$age == 0],  
              conf.level = 0.983)
```

```
##      est      lwr.ci      upr.ci  
## -5.402509 -7.479059 -3.298164
```

```
HodgesLehmann(df$outcome[df$group == 1 & df$age == 1],  
              df$outcome[df$group == 2 & df$age == 1],  
              conf.level = 0.983)
```

```
##      est      lwr.ci      upr.ci  
## -3.204365 -4.797497 -1.397309
```

```
HodgesLehmann(df$outcome[df$group == 1 & df$age == 1],  
              df$outcome[df$group == 3 & df$age == 1],  
              conf.level = 0.983)
```

```
##      est      lwr.ci      upr.ci  
## -7.287141 -8.749119 -5.665037
```

```
HodgesLehmann(df$outcome[df$group == 2 & df$age == 1],  
              df$outcome[df$group == 3 & df$age == 1],  
              conf.level = 0.983)
```

```
##      est      lwr.ci      upr.ci  
## -4.068798 -5.736961 -2.477672
```
